**Table 8 Carfilzomib Dose Modifications for Non-Hematologic Toxicity**

Event	Action to be Taken
Hypertensive crisis, or Pulmonary hypertension, or Pulmonary toxicity	Stop carfilzomib until resolved or returned to baseline. Consider whether to restart carfilzomib based on a benefit/risk assessment.
Other non-hematologic toxicity assessed as carfilzomib-related $\geq$ Grade 3	Hold dose until toxicity resolves to $\leq$ Grade 1 or baseline. Restart at 1 dose decrement.

## **6.4. Management of Carfilzomib-Related Events**

### **6.4.1. Cardiopulmonary Disorders**

New or worsening cardiac failure (e.g., congestive cardiac heart failure, pulmonary edema, and decreased ejection fraction), myocardial ischemia, and myocardial infarction have occurred following administration of carfilzomib. Death due to cardiac arrest has occurred within a day of carfilzomib administration, and fatal outcomes have been reported with cardiac failure and myocardial infarction.

While adequate hydration is required prior to dosing in Cycle 1, all subjects should be monitored for evidence of volume overload, especially subjects at risk for cardiac failure. The total volume of fluids may be adjusted as clinically indicated in subjects with baseline cardiac failure or who are at high risk for cardiac failure.

Withhold carfilzomib for Grade 3 or 4 cardiac events until recovery and consider whether to restart carfilzomib at 1 dose level reduction based on a benefit/risk assessment.

### **6.4.2. Pulmonary Hypertension**

In Phase 2 studies, pulmonary arterial hypertension was reported in 2% of subjects treated with carfilzomib and was Grade 3 or greater in less than 1% of subjects. In the pooled safety data from studies where carfilzomib was used in combination with lenalidomide-dexamethasone and in monotherapy studies (with or without dexamethasone) (N = 1581), events within the narrow pulmonary hypertension standardized Medical Dictionary for Regulatory Activities (MedDRA) query were reported in 1.1% of subjects. However, the incidence of pulmonary hypertension was similar across treatment groups in randomized, controlled studies where carfilzomib was used in combination with lenalidomide-dexamethasone and also in monotherapy studies (with or without dexamethasone). Therefore, a causal relationship with carfilzomib has not been demonstrated and pulmonary hypertension is considered an important potential risk.

Patients with New York Heart Association Class III and IV heart failure, myocardial infarction in the preceding 6 months, and conduction abnormalities uncontrolled by medications were excluded from clinical studies with carfilzomib, as they may be at greater risk of cardiopulmonary complications.

Monitor subjects for signs and symptoms of pulmonary hypertension. Evaluate with cardiac imaging and/or other tests as indicated. Withhold carfilzomib until resolved or returned to baseline and consider whether to restart carfilzomib based on a risk/benefit assessment.

#### **6.4.3. Acute Renal Disorder**

Cases of acute renal failure have been reported in subjects who received carfilzomib. Acute renal failure was reported more frequently in subjects with advanced relapsed and refractory multiple myeloma who received carfilzomib monotherapy. This risk was increased in subjects with a decrease in estimated creatinine clearance, calculated using Cockcroft and Gault equation, prior to receiving carfilzomib. Monitor renal function with regular measurement of the serum creatinine and/or estimated creatinine clearance. Reduce or withhold dose as appropriate.

#### **6.4.4. Tumor Lysis Syndrome**

Cases of TLS, including fatal outcome, have been reported in subjects who received carfilzomib. Subjects with a high tumor burden should be considered to be at greater risk for TLS. Ensure that subjects are well hydrated before administration of carfilzomib in Cycle 1 and in subsequent cycles as needed. Uric acid-lowering drugs should be considered in subjects at high risk for TLS. Monitor for evidence of TLS during treatment, including regular measurement of serum electrolytes, and manage promptly. Interrupt carfilzomib until TLS is resolved.

#### **6.4.5. Infusion Reactions**

Infusion reactions, including life-threatening reactions, have been reported in subjects who received carfilzomib. Symptoms may include fever, chills, arthralgia, myalgia, facial flushing, facial edema, vomiting, and weakness, shortness of breath, hypotension, syncope, chest tightness, or angina. These reactions can occur immediately following or up to 24 hours after administration of carfilzomib. Administer dexamethasone prior to carfilzomib either as premedication or as part of combination therapy to reduce the incidence and severity of reactions.

#### **6.4.6. Thrombocytopenia**

Carfilzomib causes thrombocytopenia with platelet nadirs observed between Day 8 and Day 15 of each 28-day cycle with recovery to baseline platelet count by the start of the next cycle. Monitor platelet counts frequently during treatment with carfilzomib. Reduce or withhold dose as appropriate.

#### **6.4.7. Hepatic Toxicity**

Cases of hepatic failure, including fatal cases, have been reported. Carfilzomib can cause elevations of serum transaminases. Monitor liver enzymes regularly. Reduce or withhold dose as appropriate.

#### **6.4.8. Thrombocytopenic Thrombotic Purpura/Hemolytic Uremic Syndrome**

Cases of thrombocytopenic thrombotic purpura/hemolytic uremic syndrome (TTP/HUS) including those with fatal outcome have been reported in subjects who received carfilzomib. Monitor for signs and symptoms of TTP/HUS. If the diagnosis is suspected, stop carfilzomib and manage per standard of care including plasma exchange as clinically appropriate. If the diagnosis of TTP/HUS is excluded, carfilzomib can be restarted. The safety of reinitiating carfilzomib therapy in subjects previously experiencing TTP/HUS is not known.

#### **6.4.9. Posterior Reversible Encephalopathy Syndrome**

Posterior reversible encephalopathy syndrome (PRES), formerly termed reversible posterior leukoencephalopathy syndrome (RPLS), is a rare neurological disorder, which can present with seizure, headache, lethargy, confusion, blindness, altered consciousness, and other visual and neurological disturbances, along with hypertension.

The diagnosis is confirmed by neuro-radiological imaging. If diagnosed early and treated, the symptoms of PRES may be reversed. Cases of PRES have been reported in subjects receiving carfilzomib. Discontinue carfilzomib if PRES is suspected. The safety of reinitiating carfilzomib therapy in subjects previously experiencing PRES is not known.

### **7. STUDY ASSESSMENTS AND EVALUATIONS**

All patients should visit the study center on the days specified within this protocol. The Schedule of Assessments for this trial is shown in Appendix E.

#### **7.1. Comprehensive Metabolic Profile (CMP)**

The following laboratory tests should be performed for each patient for assessment of CMP:

- glucose
- blood urea nitrogen (BUN)
- creatinine
- sodium
- potassium
- chloride
- calcium

- carbon dioxide (CO2)
  - alkaline phosphatase
  - AST (SGOT)
  - ALT (SGPT)
  - total bilirubin
  - total protein
  - albumin
- plus*
- magnesium
  - phosphorus

## 7.2. Baseline Assessment

All patients must have the following assessments performed before receiving their first dose of protocol therapy (labs may be obtained up to 72 hours prior to treatment):

- Obtain Signed Consent Form
- Medical history
- Physical examination, including measurement of vital signs (blood pressure, height, pulse, and respiratory rate) and weight [BSA]. Height will be obtained only at baseline.
- ECOG PS (Appendix A)
- Complete blood count (CBC )3-part differential and platelets
- CMP (see Section 7.1.) plus magnesium and phosphorus
- Uric acid
- LDH
- PT/PTT/INR
- Chest X-ray (repeat if/when clinically indicated)
- 12- lead ECG
- MUGA or ECHO with calculated left ventricular ejection fraction (LVEF) (repeat if/when clinically indicated)
- Serum or urine pregnancy test (for women of childbearing potential)
- Bone marrow biopsy/aspiration (including flow cytometry, cytogenetics and FISH for the following chromosomal abnormalities: 1q amplification, 1p del, t(4;14), t(11;14), t(14,16) or 17p del
- Skeletal survey
- Serum free light chain
- Serum immunoglobulin G, A, M
- Serum  $\beta$ -2 microglobulin
- SPEP and immunofixation
- UPEP and immunofixation requiring a 24-hour urine sample collection
- Record concomitant medications

The baseline assessments described in Appendix E will be collected prior to the initiation of treatment. The physical examination, ECOG PS, CBC, CMP, uric acid and pregnancy test should be done <7 days prior to initiation of treatment. All other assessments should be performed ≤4 weeks prior to initiation of treatment.

### **7.3. Study Treatment Period**

#### **7.3.1. Cycle 1 Day 1, 2, 5, 8, 9, 15, 16**

- Vital signs (blood pressure, weight, pulse, and respiratory rate) at each treatment visit.
- Adverse event evaluation

#### **7.3.2. Cycle 1 Day 1**

- Physical examination, including measurement of vital signs (blood pressure, pulse, and respiratory rate) and weight.
- ECOG PS (Appendix A)
- 12-lead ECGs - three ECGs will be obtained 5-10 minutes apart before the patient takes panobinostat and repeated three hours later (x 3) 5-10 minutes apart.
- CBC, 3-part differential and platelets (-3 to Day 1 window allowed)
- CMP (see Section 7.1.) plus magnesium and phosphorus (-3 to Day 1 window allowed)
- Uric acid (-3 to Day 1 window allowed)
- LDH
- PT/PTT/INR (if medically indicated or if patient is receiving warfarin or other anti-coagulant)
- Adverse event evaluation
- Record concomitant medications

#### **7.3.3. Cycle 1 Day 5**

- 12-lead ECGs – three will be obtained 5-10 minutes apart before the patient takes panobinostat and repeated three hours later (x 3) 5-10 minutes apart.
- Vital signs (blood pressure, weight, pulse, and respiratory rate)

#### **7.3.4. Cycle 1 Day 8 and 15**

- Medical history (Day 15 only)
- Physical examination (Day 15 only)
- ECOG PS (Appendix A)

- Vital signs (blood pressure, weight, pulse, and respiratory rate)
- CBC, 3-part differential and platelets (-3 to Day 1 window allowed)
- CMP (see Section 7.1.) plus magnesium and phosphorus (-3 to Day 1 window allowed)
- Uric acid (-3 to Day 1 window allowed)
- LDH
- PT/PTT/INR (if medically indicated or if patient is receiving warfarin or other anti-coagulant)
- Adverse events assessment
- Record concomitant medication

#### **7.3.5. Cycle 2 and Beyond - Day 1, 8 and 15**

- Medical history (Day 1 only)
- Physical examination (Day 1 only)
- Measurement of vital signs (blood pressure, pulse, and respiratory rate and weight)
- ECOG PS (Day 1 only) (Appendix A)
- CBC, 3-part differential and platelets (-3 to Day 1 window allowed)
- CMP (see Section 7.1.) plus magnesium and phosphorus (Day 1 only) (-3 to Day 1 window allowed)
- Uric acid (if clinically indicated) (-3 to Day 1 window allowed)
- LDH (if clinically indicated)
- PT/PTT/INR (Day 1 only; if medically indicated or if patient is receiving warfarin or other anti-coagulant)
- 12-lead ECG (Day 1 only if no previous problems with QTc prolongation)
- Adverse event evaluation
- Record concomitant medications

#### **7.4. Re-Staging – 4 Weeks (-7 to Day 1 window allowed)**

- Bone marrow biopsy/aspiration (including cytogenetics and FISH for the following chromosomal abnormalities: 1q amplification, 1p del, t(4;14), t(11;14), t(14,16) or 17p del) (REQUIRED ONLY TO DOCUMENT A CR)
- Serum free light chain
- Serum immunoglobulin G, A, M
- SPEP and immunofixation
- UPEP and immunofixation requiring a 24-hour urine sample collection

At any point in this treatment, patients suspected of PD will have response assessed again to confirm disease progression (i.e. 2 sets of response assessments at least 1

week apart). The outcomes will be reviewed by the study chair before the patient is removed from the study. After the second set of response assessments, if disease progression is confirmed, the date of the first set of response assessments should be recorded as the progression date.

## **7.5. End of Study Treatment**

The following assessments will be performed for each patient within 30 days after treatment ends according to protocol guidelines.

- Physical examination, including measurement of vital signs
- Update Medical history
- ECOG Performance Status
- CBC, 3-part differential and platelets
- CMP (see Section 7.1.) plus magnesium and phosphorus
- Uric acid (if clinically indicated)
- LDH (if clinically indicated)
- 12-lead ECG
- Serum free light chain
- Serum immunoglobulin G, A, M
- SPEP and immunofixation
- UPEP and immunofixation requiring a 24-hour urine sample collection
- Adverse event assessment
- Concomitant medication review

Patients who discontinue treatment prior to disease progression will have the study assessments performed as described in Appendix E.

If treatment is discontinued because of toxicity or any other reason(s) at a treatment visit and no study treatment is administered, that visit may fulfill the End of Treatment Visit.

After withdrawal from or completion of protocol treatment, patients must be followed for adverse events for 30 calendar days after the last dose of study drug.

## **7.6. Follow-Up**

### **7.6.1. Follow-Up for Patients who Discontinue Treatment Prior to Disease Progression**

Patients who discontinue study treatment prior to the occurrence of disease progression will be followed every 3 months from date of last dose of study drug during years 1 and 2, every 6 months during years 3-5, and annually thereafter for toxicity, disease progression, and survival. Appropriate disease assessments will be performed every 3 months during years 1 and 2 after study discontinuation, and every 6 months during

years 3, 4, and 5. After disease progression is documented, patients will be followed every 3 months as specified in Section 7.5.2. Assessments at these visits will be performed as described in Appendix E.

## **7.6.2. Follow-Up After Disease Progression**

After disease progression is documented, patients will be followed every 3 months. Assessments during this time will be performed as described in Appendix E.

### **7.6.2.1. Pregnancy test**

All females of childbearing potential should complete a serum or urine pregnancy test within 7 days prior to the administration of trial drug on day 1 of cycle 1.

Postmenopausal women must have been amenorrheic for  $\geq 12$  months in order to be considered “of non-childbearing potential”.

## **8. DRUG FORMULATION, AVAILABILITY, ADMINISTRATION, AND TOXICITY INFORMATION**

### **8.1. Panobinostat**

#### **8.1.1. Panobinostat Formulation**

Panobinostat (also known as LBH589) will be provided by Novartis. Oral panobinostat will be supplied as 5-mg, 15-mg, or 20-mg pink/opaque-colored, hard gelatin capsules.

#### **8.1.2. Panobinostat Drug Supply**

Panobinostat for use in this study will be supplied to the Sponsor, SCRI Development Innovations, LLC (SCRI Innovations), by Novartis. Study sites will obtain panobinostat from Sponsor designee(s) at SCRI Innovations per instructions provided to participating study sites.

Accountability for the drug at all study sites is the responsibility of the principal investigator at each study site. The investigator will ensure that the drug is used only in accordance with this protocol. Drug accountability records indicating the drug’s delivery date to the site (if applicable), inventory at the site (if applicable), use by each patient, and return to SCRI Innovations or disposal of the drug (if applicable and if approved by SCRI Innovations) will be maintained by the clinical site. Accountability records will include dates, quantities, lot numbers, expiration dates (if applicable), and patient numbers. Once panobinostat is shipped to a site, it may not be shipped or shared with another site or patient.

All material containing panobinostat will be treated and disposed of as hazardous waste in accordance with governing regulations.

### 8.1.3. Storage and Stability

The storage conditions for study drug will be described on the medication label.

### 8.1.4. Administration

Oral panobinostat capsules should be administered as follows:

- Patients should be instructed to take their three times a week oral dose of panobinostat at the same time on each dosing day (e.g. day 1, 3, and 5). Doses should be separated by a minimum of 30 hours.
- Dose may be taken with or without food.
  - In the event that the patient does not take the daily dose at the specified routine time, unrelated to toxicity (for example, the patient forgets), but the dose can be taken within 12 hours of the specified time, then s/he may take the daily dose at that time. If more than 12 hours have passed, that day's dose should be withheld, and the patient should wait to take panobinostat until the next scheduled treatment day. The patient should then continue treatment with the original dosing schedule. This should be clearly documented on the Dosage Administration Record CRF by a member of the research team.
  - Each dose of panobinostat should be taken with a glass (approximately 240 mL) of water. Patients should be instructed to swallow the capsules whole and not chew them.
  - If vomiting occurs during the course of treatment, then no re-dosing of the patient is allowed before the next scheduled dose.
  - Patients must avoid grapefruits, grapefruit juice, Seville (sour) oranges and Seville orange juice during the entire study period.

Note: Food influence on panobinostat PK was evaluated in patients with advanced cancer who received 20 mg panobinostat twice a week and were randomized to receive 1 of 6 treatment sequences where PK was evaluated weekly under fasting, high fat, and normal breakfast conditions CLBH589B2111. The overall exposure and inter-patient variability (CV 59%) in 34 patients remained unchanged with or without food, whereas  $C_{max}$  was transiently reduced (<45%) by food (i.e., both normal and high fat breakfast). Since the overall extent of absorption was not altered by food, food is unlikely to significantly impact panobinostat systemic exposure in cancer patients.

### 8.1.5. Panobinostat Toxicities

Most frequently reported adverse events (occurred in at least 30% of patients):

1. Fatigue and weakness
2. Decreased appetite, anorexia or altered taste
3. Diarrhea which can lead to dehydration, loose stools, abdominal cramping
4. Nausea and vomiting

5. Thrombocytopenia
6. Leukopenia
7. Anemia

Additional side effects that have been observed in ongoing clinical trials:

1. Weight loss
2. QTc prolongation, atrial fibrillation
3. Changes in thyroid function
4. Changes in blood electrolytes and glucose
5. Increase in creatinine levels
6. Other side effects reported include: back, extremity, muscle, joint and bone pain, headache, coughing, breathing problems including shortness of breath, anxiety, depression, dizziness, constipation, fever, abdominal pain, swelling in the legs or eye, itchiness, peripheral ischemia, chest pain, loss of feeling or tingling in the arms and legs, inflammation of nose, throat and lining of the mouth.

#### **8.1.6. Panobinostat Precautions and Risks**

Patients must avoid grapefruit or grapefruit juice and Seville (sour) oranges or juice during the entire study.

Medications known to be substrates of the isoenzyme CYP2D6 should be avoided if possible, since panobinostat can inhibit isoenzyme CYP2D6 at low micromolar ranges.

#### Drugs that can inhibit/induce CYP3A4/5

##### Drugs that can inhibit CYP3A4/5

Panobinostat is metabolized *in vitro* by CYP3A4/5. A clinical drug-drug interaction study with ketoconazole and panobinostat has recently been completed. The less than 2-fold increase in panobinostat AUC upon co-administration with ketoconazole suggests that CYP3A contribution to the total clearance of panobinostat is low. The observed interaction is not considered clinically relevant, as panobinostat doses at least 2-fold greater than 20 mg (40 and 60 mg) have been safely administered in patients. CYP3A4 inhibitors should have no major impact on the exposure of panobinostat and may be co-administered when medically necessary.

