### **5.4. Concomitant Medications**

Patients must be instructed not to take any additional medications (including over-the-counter products) during the trial without prior consultation with the study physician. All medications taken within 30 days of screening should be noted. If concomitant therapy must be added or changed, the reason and name of the drug/therapy should be recorded.

In general, the use of any concomitant medication/therapies deemed necessary for the care of the patient are allowed, including drugs given prophylactically (e.g. antiemetics) with the following exceptions:

- Any medications which may cause QTc prolongation or induce Torsades de Pointes should not be used (see Appendix F). Dolasetron is contraindicated while on treatment with Panobinostat.
- Any medications that have the potential to alter serum electrolytes (e.g. diuretics) should be monitored very closely for electrolyte abnormalities as these can contribute to the risk of QTc prolongation and vent.
- No other investigational therapy should be given to patients.
- Allopurinol (in subjects at risk for TLS due to high tumor burden) is optional and will be prescribed at the study physician's discretion. These patients may receive allopurinol 300 mg PO BID (Cycle 1 Day -2, Day -1), continuing for 2 days after Cycle 1 Day 1 (total of 4 days), then reduce dose to 300 mg PO QD, continuing through Day 17 of Cycle 1. Allopurinol dose should be adjusted according to the package insert.

- No anticancer agents other than the study medications administered as part of this study protocol should be given to patients. If such agents are required for a patient then the patient must first be withdrawn from the study.
- Leukocyte growth factors (e.g. G-CSF and GM-CSF) are not to be administered prophylactically but may be prescribed by the study physician for severe neutropenia if this is thought to be appropriate.
- Medications known to be substrates of the isoenzyme CYP2D6 should be avoided if possible, as panobinostat can inhibit isoenzyme CYP2D6 at low micromolar ranges (see Appendix G).
- Medications, food, and herbal preparations known to be strong inducers or inhibitors of CYP3A4 should be avoided if possible (see Appendix G).

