## Appendix 6: Drugs That Prolong QT Interval and/or Induce Torsades De Pointes

Patients who are receiving treatment with any of the medications in the table below, and cannot either discontinue form this treatment or switch to a different medication prior to study enrollment, will be excluded from this study. Patients may not begin study treatment while receiving any of the medications identified below. If a patient must receive these drugs, the patient should be removed from study. Enrolling patients should be off study treatment at least 72 hours prior to taking the first dose of a medication listed below. This is not a comprehensive list. A complete list may be found and updated at the following web address: [qtdrugs.org/medical-pros/drug-lists/drug-lists.htm](http://qtdrugs.org/medical-pros/drug-lists/drug-lists.htm).

---

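### Sections 8.1.6 and 5.1.2.1 permit whole drug classes without the QT limit set by Section 5.4 and Appendix F; eight drugs printed in Appendix F fall in those classes

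*Combined protocol and SAP*

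**What the plan says.** **The restriction.** Section 5.4 opens with a general allowance: "In general, the use of any concomitant medication/therapies deemed necessary for the care of the patient are allowed, including drugs given prophylactically". Exceptions follow, and the first reads "Any medications which may cause QTc prolongation or induce Torsades de Pointes should not be used (see Appendix F"). Appendix F (headed Appendix 6 where it is printed) adds: "If a patient must receive these drugs, the patient should be removed from study". It also says of itself: "This is not a comprehensive list". Exclusion criterion 7 in Section 3.2 applies the same limit at entry.

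**Permission 1.** Section 8.1.6, under drugs that can inhibit CYP3A4/5, reports that "A clinical drug-drug interaction study with ketoconazole and panobinostat has recently been completed". From a less than two-fold rise in panobinostat AUC it concludes that "CYP3A4 inhibitors should have no major impact on the exposure of panobinostat and may be co-administered when medically necessary".

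**Permission 2.** Section 5.1.2.1 allows antibiotic prophylaxis with ciprofloxacin or any other fluoroquinolone if clinically indicated. Trimethoprim/sulfamethoxazole is the alternative when fluoroquinolones are contraindicated (the text prints a slip for this word).

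Neither permission refers to Section 5.4 or Appendix F. Elsewhere in Section 8.1.6, QTc comes up only in connection with serum electrolytes.

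**The concern.** For a patient with a medical need for a listed CYP3A4 inhibitor, the stated rules point in opposite directions. Section 8.1.6 says the drug may be given; Section 5.4 says it should not be used; Appendix F says the patient should come off study. A study physician who consults only the section on panobinostat interactions, or only the carfilzomib prophylaxis advice, could add a restricted drug in good faith.

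The reasoning in Section 8.1.6 does not resolve this. It concerns panobinostat exposure, and a small change in exposure says nothing about a second drug's own effect on QTc. Section 5.1.1.1 itself gives observed QTc prolongation in several patients on panobinostat as the reason for intensive ECG monitoring.

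What is at stake is patient safety and uniform handling across sites.

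**Working it through.** The plan states no figure on this point, so there is none to reproduce. The check is a comparison of printed lists.

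**Step 1. Size of the Appendix F list.** By heading: antiarrhythmics 7, antibiotics 5, antipsychotics 7, antidepressants 6, azole antifungals 2, antimalarials 2, antiemetics 5, miscellaneous 6.
7 + 5 + 7 + 6 + 2 + 2 + 5 + 6 = 40.

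**Step 2. Overlap with CYP3A4 inhibitors.** The inhibitor column of Appendix G (headed Appendix 7 where it is printed) has 19 entries. Five are also in Appendix F: amiodarone, clarithromycin, erythromycin, itraconazole, ketoconazole.

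**Step 3. Overlap with fluoroquinolones.** Appendix F prints three: gatifloxacin, moxifloxacin, sparfloxacin. Ciprofloxacin, the only one named in Section 5.1.2.1, is not printed there.

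**Step 4. Total.** No drug is in both groups, so 5 + 3 = 8. This uses the column headed as inhibitors. Appendix G also has a substrate column labelled as competitive inhibition; counting that as well would add cisapride, haloperidol, methadone, pimozide, quinidine and tacrolimus, giving 8 + 6 = 14. Eight is the narrower and safer count.

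**Step 5. The rules set side by side for ketoconazole.**

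| Place | Instruction |
|---|---|
| Section 8.1.6 | CYP3A4 inhibitors may be given if medically needed |
| Section 5.4, bullet on strong CYP3A4 inhibitors | avoid where possible (Appendix G marks ketoconazole as strong) |
| Section 5.4, QT bullet | should not be used |
| Appendix F | if it must be given, the patient leaves the study |

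These are different strengths of instruction for one drug, and no sentence says which prevails. The same holds for itraconazole, also marked strong in the inhibitor column. For erythromycin and amiodarone, which carry no strong mark, the QT restriction stands alone against Section 8.1.6.

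**Step 6. A lesser inconsistency, counted separately.** The CYP2D6 table in Appendix G gives monitoring and dose-titration advice, should its drugs be used, for ten drugs that are in Appendix F: haloperidol, risperidone, thioridazine, chlorpromazine, venlafaxine, amitriptyline, desipramine, imipramine, dolasetron and ondansetron. For one of them Section 5.4 is explicit: "Dolasetron is contraindicated while on treatment with Panobinostat".

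**The case against.** The strongest reply is that Section 5.4 already settles the matter. It is the operative section on concomitant medication, and it allows necessary and prophylactic drugs subject to exceptions. A medically necessary CYP3A4 inhibitor or an indicated fluoroquinolone fits the general allowance and is then caught by the QT exception. On a reading of the whole protocol, that is right.

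Other controls also stand:

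- Exclusion 7 screens patients at entry.
- Section 5.4 requires that "Patients must be instructed not to take any additional medications (including over-the-counter products) during the trial without prior consultation with the study physician".
- Section 5.4 separately discourages strong CYP3A4 inhibitors, and Section 5.1.2.1 offers a non-fluoroquinolone alternative.
- Concomitant drugs are recorded on Days 1, 8 and 15.
- Triplicate ECGs are taken before and after dosing on Days 1 and 5 of Cycle 1, then a single pre-dose ECG on Day 1 of later cycles.
- In the 480 to under 500 msec band, Table 7 permits the same dose when a concomitant drug is blamed, but only after repeat triplicate ECGs meet the dosing criteria. A Day 5 pre-dose finding also brings a delay of at least 3 days; a post-dose finding brings hourly ECGs or telemetry.
- Section 1.2.3 reports 2,200 ECGs in the Phase Ib bortezomib combination with no QTcF above 480 msec.

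These lower the risk without removing the conflict. The study physician who must be consulted is the person the two permissions address. From Cycle 2 a drug started mid-cycle may meet no scheduled ECG before the next Day 1, and after eight cycles without significant prolongation ECG monitoring becomes optional.

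A reader might infer more than the documents support:

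- *That the protocol authorises ketoconazole by name.* It is the probe drug of the interaction study; the permission sentence names no drug.
- *That the CYP2D6 table permits ten more restricted drugs.* Its advice is conditional, and Sections 5.4 and 8.1.6 say to avoid CYP2D6 substrates where possible.
- *That the interval between medication reviews caps exposure.* A review records the drug; whether it is then stopped depends on which section the physician follows.

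**Conclusion.** The point holds as a minor safety inconsistency. Two class permissions omit a QT restriction stated elsewhere, and eight drugs printed in Appendix F fall within them: five as CYP3A4 inhibitors and three as fluoroquinolones. The count assumes the printed lists and the column headed as inhibitors.

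It is not a missing safeguard, because the restriction is stated in exclusion 7, Section 5.4 and Appendix F. Removal from study rests on Appendix F alone; for QT drugs Section 5.4 says only that they should not be used. Eight out of 40 should not be read as a risk or a proportion, since Appendix F describes its list as incomplete. The documents do not show how often a restricted drug would be given, and they support no claim about the response, time-to-event or tolerability results.

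**What to change.** 1. In Sections 8.1.6 and 5.1.2.1, add after each permission: *except any drug that may prolong QTc or induce Torsades de Pointes (Section 5.4, Appendix F and its updated list)*. Tie the exception to QT-prolonging drugs in general, not only to those printed in Appendix F, because that list is incomplete and Section 5.4 is not confined to it.
2. In Section 5.4, state that the QT restriction prevails over Sections 5.1.2.1 and 8.1.6 and Appendix G.
3. Optionally, flag in Appendix G the five overlapping CYP3A4 inhibitors and the ten overlapping CYP2D6 substrates, with a pointer to Section 5.4 and Appendix F.

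The cost is a wording amendment and a note to sites. No visits, procedures or patients are added. The downside is a slightly narrower choice of prophylactic antibiotics, azole antifungals and other supportive drugs, which Section 5.4 and Appendix F already imply.
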